Preliminary data also suggest that parents may not be aware of their child's risk related to nutrition and sleep. Most parents are confident in their knowledge of nutrition recommendations (72%) and were "not at all concerned" with their child's consumption of fruits (67%) or vegetables (53%). Similarly, most parents were also confident in their knowledge of sleep recommendations (89%), yet only 22% considered their child's sleep to be problematic. These data signal a disconnect between parental confidence and/or knowledge of healthy behaviors and reports of their child's behavior. We plan to measure child behavior change in each Institute of Medicine obesity prevention priority over time and identify associations with parental knowledge, readiness for change, empowerment, and activation.

Study Objectives

[figure not shown]
This proposed pilot RCT aims:

- 1) To determine the feasibility of the Pro-PEAR intervention in terms of recruitment, randomization, retention, adherence, and acceptability.
- 2) Estimate the effects of the Pro-PEAR intervention on parent reported child health behaviors in each IOM obesity prevention area (nutrition, physical activity, sedentary behavior, sleep) over time as compared to an enhanced usual care group.

Study Design & Methods

We will recruit 24 parent/child dyads from the Down Syndrome Center of Western PA to participate in a pilot RCT. Inclusion criteria for child participants are being between the ages of 12-36 months and having a diagnosis of Down syndrome; parent participants must be ≥ 18 years old and able to speak English fluently. We are recruiting children 12-36 months as most children are able to self-feed and sleep through the night at this time, yet it precedes the rapid weight gain observed among children with Down syndrome.⁷ Sample size was determined based on prior recruitment efforts and data on number of children within this age range served at the clinic (~100). We will use a 2:1 randomization ratio for assignment to intervention versus control group status to gain more experience using the newly developed PrO-PEAR intervention (see Figure 3). Child health behavior in the areas of nutrition, physical activity, sedentary behavior, and sleep will be reported by parents, in addition to general health status and potential mechanisms of behavior change at baseline, 3-months (post-intervention) and 6-months (follow-up). We will track physical growth via chart review.

Figure 1. Randomization Plan

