B.2.1.4. Data Analysis. Feasibility data will be assessed using descriptive statistics (e.g., frequencies, means, percentages) and compared to a priori benchmarks. We will calculate bivariate correlations between demographics, intervention adherence, and outcomes to identify potential confounders or factors that may influence response to treatment. We will estimate effect sizes (Cohen's d) of child health behaviors and parental factors (knowledge, readiness, empowerment, activation) over time and between groups. Finally we will explore associations (bivariate correlations) between potential mechanisms of change (parental factors) and child behavior change scores. Parental factors significantly associated with child behavior change will be analyzed using multiple linear regression to identify significant predictors of child health behavior.

Eligibility Criteria

Inclusion criteria for child participants are being between the ages of 12-36 months and having a diagnosis of Down syndrome; parent participants must be ≥ 18 years old and able to speak English fluently. We are recruiting children 12-36 months as most children are able to self-feed and sleep through the night at this time, yet it precedes the rapid weight gain observed among children with Down syndrome.

Statistical Considerations

Feasibility data will be assessed using descriptive statistics (e.g., frequencies, means, percentages) and compared to a priori benchmarks. We will calculate bivariate correlations between demographics, intervention adherence, and outcomes to identify potential confounders or factors that may influence response to treatment. We will estimate effect sizes (Cohen's d) of child health behaviors and parental factors (knowledge, readiness, empowerment) over time

and between groups. Finally we will explore associations (bivariate correlations) between potential mechanisms of change (parental factors) and child behavior change scores. Parental factors significantly associated with child behavior change will be analyzed using multiple linear regression to identify significant predictors of child health behavior.

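### The plan names Cohen's d with no small-sample correction for a trial of about 16 v 8 dyads; Hedges' g with a named SD would remove a small upward bias at no cost

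*Combined protocol and SAP*

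**What the plan says.** The second aim, under Study Objectives, is to "Estimate the effects of the Pro-PEAR intervention on parent reported child health behaviors in each IOM obesity prevention area", compared with enhanced usual care. Two paragraphs say how: Data Analysis (section B.2.1.4) and Statistical Considerations. Each contains the sentence that begins "We will estimate effect sizes (Cohen's d) of child health behaviors and parental factors". The first continues "knowledge, readiness, empowerment, activation) over time and between groups". The second has the same sentence with a shorter list of parental factors: "knowledge, readiness, empowerment) over time", and again between groups.

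Study Design & Methods gives the size: "We will recruit 24 parent/child dyads from the Down Syndrome Center of Western PA to participate in a pilot RCT". It also gives the allocation: "We will use a 2:1 randomization ratio for assignment to intervention versus control group status". Outcomes are collected "at baseline, 3-months (post-intervention) and 6-months (follow-up").

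Three things are not stated in either analysis paragraph:

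- a small-sample correction to d;
- the SD that standardizes each contrast;
- whether the over-time d is computed in each arm or over all dyads.

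**The concern.** Cohen's d divides a mean difference by a sample SD. In small samples the expected value of one over that SD exceeds one over the true SD, so d lands too far from zero on average. The excess is a fixed proportion that depends only on the degrees of freedom behind the SD. It vanishes when the true effect is zero, and otherwise always pushes the same way.

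This matters here because d is the only measure the plan names for comparing the groups under the second aim, and the samples are small. The bias would run in the same direction through every behavior and parental factor with a non-zero effect, so it would not average out across the results table. If within-arm values were printed side by side, the smaller control arm would be flattered more than the PrO-PEAR arm.

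**Working it through.** **Inputs**

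- Total of 24 dyads and 2:1 allocation (Study Design & Methods). 24 × 2/3 = 16 and 24 × 1/3 = 8. The arm sizes are derived, not printed.
- The total rests on feasibility: "Sample size was determined based on prior recruitment efforts and data on number of children within this age range served at the clinic". No alpha, power, SD or target effect is given, so there is no power calculation to reproduce.
- A true d of 0.5 is my illustration, not a figure from the plan.

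**Formula**

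For normal data, E[d] = δ / J, where J = Γ(df/2) / [√(df/2) × Γ((df − 1)/2)]. The usual approximation is J ≈ 1 − 3/(4 × df − 1). Expected inflation is 1/J − 1.

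| Contrast and SD | df | J exact | J approx. | Inflation | E[d] if true d = 0.5 |
|---|---|---|---|---|---|
| Between groups, pooled SD | 16 + 8 − 2 = 22 | 0.9655 | 1 − 3/87 = 0.9655 | 3.6% | 0.518 |
| Within PrO-PEAR, own SD | 16 − 1 = 15 | 0.9490 | 1 − 3/59 = 0.9492 | 5.4% | 0.527 |
| Within controls, own SD | 8 − 1 = 7 | 0.8882 | 1 − 3/27 = 0.8889 | 12.6% | 0.563 |

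The approximation is within 0.001 of the exact factor in each row.

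**Does the 2:1 split cause it?**

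- Between groups with a pooled SD, no. A 12 + 12 split also has 22 df and the same 3.6%.
- Within arms, the split makes the inflation unequal. At 12 + 12 each arm would have 11 df, J = 0.930 and 7.5% inflation.

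**Size beside sampling error, at a true d of 0.5**

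- Between groups: SE = √(1/16 + 1/8 + 0.25/44) = 0.44. Bias = 0.018, about 4% of the SE.
- Within PrO-PEAR: SE = √(1/16 + 0.25/30) = 0.27. Bias = 0.027, about 10%.
- Within controls: SE = √(1/8 + 0.25/14) = 0.38. Bias = 0.063, about 17%.

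**Dependence on the SD chosen**

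A simulation of 400,000 replicates per setting, with pre/post correlations of 0.3, 0.5 and 0.7, gave the following.

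- Change-score SD and baseline SD from a single arm reproduced the within-arm inflation in the table.
- An averaged pre/post SD gave mean d of 0.514 to 0.519 at n = 16 (about 3% to 4%) and 0.532 to 0.543 at n = 8 (about 6% to 9%).
- The choice of SD changes the target itself. With a true baseline-SD d of 0.50, the true change-score d is 0.50/√(2 − 2ρ): 0.42 at ρ = 0.3 and 0.65 at ρ = 0.7.
- With the control-arm SD as the between-group standardizer, df is 7 and the inflation is 12.6%, not 3.6%.

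**The case against.** The strongest reply is that this hardly matters. The contrast that answers the second aim is between groups, and its bias is about 4% of its standard error. Anyone given d, the arm sizes and the SD can apply the correction later. All of that is true and it sets the priority. It does not justify leaving a known bias in the reported figures when removing it takes one multiplication.

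A second reply is that the correction cannot be applied as the plan stands, because J needs the degrees of freedom of an SD that the plan does not name. This stands, and it adds a clause to the fix. The choice of SD also shifts d by more than the bias does.

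A third is that the lack of a correction is inferred from silence. That is fair: the analysts may intend one. Cohen's d ordinarily means the uncorrected statistic, though, so the text needs clarifying either way.

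A reader might also infer more than the documents support:

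- *That the two arms' effect sizes would be on different scales.* Unequal finite-sample bias does not change the scale; the choice of standardizing SD does.
- *That the 2:1 ratio distorts the between-group result.* With a pooled SD it does not, as shown by the 12 + 12 comparison.
- *That controls would certainly be inflated by 12.6%.* This needs a within-arm d on a single-arm SD, which the plan does not state. An SD pooled over both arms (22 df) would give about 3.6% throughout. No comparison of within-arm values is planned, and the gap of 0.563 − 0.527 = 0.036 would sit beside a standard error of √(0.266² + 0.378²) = 0.46.
- *That dropout to about 13 and 6 would raise the control figure to 18.9%.* The 80% retention benchmark in Table 1 concerns completed sessions, not outcome data, so those numbers are only an assumption.
- *That a later trial would be undersized.* The plan does not say that d will be used to size one. The Measures section says the data will inform optimization of the intervention.

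**Conclusion.** The point holds as a minor one. As written, the plan's effect measure is biased away from zero for any non-zero effect. The expected inflation is about 3.6% between groups with a pooled SD. It is about 5.4% (PrO-PEAR) and 12.6% (controls) only if d over time is computed within arm on that arm's own baseline or change-score SD, and less with an averaged pre/post SD.

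These figures assume that all 24 dyads are analyzed as 16 and 8, that data are roughly normal (several measures are Likert scales or a 10-item test, so they are approximate), and that no correction is intended. Imprecision is far the larger problem at this sample size, and Hedges' g does not reduce it materially. The documents do not support a claim that the arms are on different scales, that the allocation ratio biases the between-group estimate, or that a future trial would be too small. This is a free improvement, not a flaw that threatens the trial's aims.

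**What to change.** In both Data Analysis (B.2.1.4) and Statistical Considerations:

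1. Replace Cohen's d with Hedges' g, defined as d × J with J = 1 − 3/(4 × df − 1).
2. Name the SD that standardizes each contrast, over time and between groups, and say whether the over-time effect is computed per arm.
3. Use the degrees of freedom of that SD in J: 22 for a pooled two-arm SD, 15 or 7 for a single-arm baseline or change-score SD, fewer if data are missing. An averaged pre/post SD comes from the same children twice, so its df is not simply n − 1. If it is chosen, the plan should state the approximation used.

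The cost is a wording change in two paragraphs, a decision on the SD, and one multiplication per estimate. It needs no extra dyads, visits or data. Reported effects become slightly smaller.

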Study Protocol

Official Title: Promoting Health through Parent Empowerment and the Activation of Routines (Pro-PEAR)

ClinicalTrials.gov ID (NCT number): NCT05020366

Protocol Date: 12/12/2022

Scientific Background

Obesity disproportionately impacts children with Down syndrome. Despite serious comorbidities such as higher rates of type 2 diabetes and obstructive sleep apnea syndrome, obesity prevention efforts have been largely neglected within this population. As guided by the 6-SQuID framework, we: 1) defined the problem; 2) clarified causal/contextual factors; 3) identified mechanisms underlying change; and 4) identified how to most efficiently target the change mechanism. Our primary deliverable, a manualized intervention protocol for the PrO-PEAR intervention, will be optimized and tested for feasibility in this study.

Preliminary Data: The Facilitators and Barriers to Health in Young Children with Down syndrome (FaB Health Ds) survey data can help to inform intervention design and drive prioritization of intervention components. According to data collected during our pilot phase (N=33), nutrition and sleep are emerging as priority areas to target for the PrO-PEAR intervention. The World Health Organization (WHO) recommends toddlers consume 5 or more servings of fruits and vegetables per day, however, only 34% of our sample meet this recommendation per parent report. When asked how much quality sleep their child gets over a 24-hour period, less than half of all parents reported an estimate within the recommended range (11-14 hours). In contrast, most parents report that their children meet the recommendations for physical activity, in that they participate in at least 3 hours of activity each day. Most families reported meeting recommendations for sedentary behaviors, such as screen time and time spent restrained (e.g., in a device like a highchair) to 1 hour or less.

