B.2.1.3. Treatment. We will test the feasibility of delivering the PrO-PEAR intervention and our ability to randomize to an enhanced usual care group. Participants randomized to enhanced usual care will receive feedback on health behaviors after baseline assessments and continue to receive usual care therapies outside of the study. The PrO-PEAR group will complete four in-person modules with an occupational therapist, each covering an IOM obesity prevention priority area: 1) Healthy Eating; 2) Sleep; 3) Sedentary Behavior; and 4) Physical Activity. Parents in the intervention group will also receive six telehealth visits of family-based coaching to help participants understand recommendations and adopt new, healthy routines.

B.2.1.4. Measures. A priori benchmarks for recruitment, retention, adherence, data collection and acceptability have been established to test the feasibility of the PrO-PEAR intervention. Potential issues in each of these areas have been identified with possible solutions for each barrier (see Table 1). Protocol adherence will be evaluated via review of sessions using clinician documentation. Intervention acceptability will be rated using the Treatment Acceptability Questionnaire (TAQ),⁷ a valid and reliable assessment of parental intervention acceptance. Intervention completers are designated as those completing 80% of sessions (≤ 8 of 10).

Table 1. Indicators of Feasibility and Acceptability

Topic	Benchmark	Plan if Benchmark is Not Met
Recruitment	>3 parent/child dyads per month	Partner with other Ds clinics
Retention	$\geq 80\%$ of consented dyads will complete ≥ 8 sessions	Parent focus group to identify issues
Adherence	$\geq 80\%$ clinician protocol adherence during 100% of sampled sessions	Update protocol and increase training
Data Collection	$\geq 80\%$ planned assessments collected among intervention completers	Evaluate burden and reduce as needed
Acceptability	$\geq 90\%$ of parent intervention completers rate intervention as acceptable ($>28/48$ on TAQ)	Parent focus group to optimize protocol

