We will assess parent-reported child health behaviors, parental mechanisms of behavior change, and child anthropometrics and demographics over time (see Table 2). The knowledge test will be created using the World Health Organization's early childhood recommendations for obesity prevention. All other tools have been validated for use with parents of young children. For this study, we are specifically interested in parent factors that may influence behavior

change, as parents provide the opportunities, environment, structure and feedback that will determine a child's formation of healthy (or unhealthy) behaviors early in life. Data collected during this trial will inform intervention optimization to emphasize those mechanisms related to prioritized child behaviors.

Table 2. Intervention Measures

Assessment	Brief Description	Outcome
Facilitators & Barriers to Health: Down syndrome (FaB Health Ds) ⁸	100-item parent survey designed to describe habits and facilitators/barriers to health in young children with Down syndrome ($\alpha=.91$).	Parent-reported child nutrition, physical activity, sedentary behavior and sleep behaviors
Knowledge of Recommendations to Prevent Obesity in Young Children	10-item test to determine knowledge of recommendations for nutrition, activity, sedentary behavior and sleep	Parental knowledge of healthy behavior recommendations
Readiness, Efficacy, Attributions, Defensiveness, & Importance Scale – Short Form (READI-SF) ⁹	15-item Likert-scale survey in which higher scores indicate greater parental readiness to engage in treatment and readiness for change ($\alpha=.94$).	Parental readiness for change
Parent Empowerment and Efficacy Measure (PEEM) ¹⁰	20-item Brief Likert-scale and strength-based assessment of parental empowerment and efficacy ($\alpha=.92$).	Parental empowerment
Child Anthropometrics	Height, weight, body circumferences (waist, hip, arm, thigh)	Health status (growth)
Child Demographics	Age, medical diagnoses, service utilization, surgical history, race, ethnicity, household income	Health and socioeconomic status

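### The between-group Cohen's d for Aim 2 has no confidence interval, baseline adjustment or full definition; a baseline-adjusted difference with a 95% CI is a cheap improvement

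*Combined protocol and SAP*

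**What the plan says.** Aim 2 (Study Objectives) is to estimate intervention effects on parent-reported child behaviors in four areas, "over time as compared to an enhanced usual care group". Study Design & Methods schedules parent reports at baseline, 3 months and 6 months. It sets allocation ("We will use a 2:1 randomization ratio for assignment to intervention versus control group status") for 24 dyads and gives the basis for that number: "Sample size was determined based on prior recruitment efforts", together with clinic volume.

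The analysis text appears twice, under B.2.1.4 Data Analysis and under Statistical Considerations. In both places one sentence covers the Aim 2 estimate: Cohen's d "of child health behaviors and parental factors (knowledge, readiness, empowerment, activation) over time and between groups". The second copy differs only in omitting activation, which has no instrument in Table 2.

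Neither copy mentions a confidence interval or a covariate for the group effect. Neither says which follow-up the between-group d belongs to, whether it is on follow-up or change scores, or which SD divides it. Change scores and multiple regression appear only in the analyses of parental mechanisms. The correlations meant to find confounders lead to no adjusted treatment estimate.

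**The concern.** The trial is sized on recruitment and claims no power, and Aim 2 is purely an estimation aim. How precisely each effect is known is therefore a main part of the result, and a d without an interval leaves it out.

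The statistic is also not fully defined. Two follow-up times, two score types and more than one possible SD allow several values of d from the same data, and the choice could be made after the data are seen.

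Finally, the baseline value of each outcome is already collected but does not enter the effect estimate. The issue is precision and definition. Under randomization the unadjusted contrast is not biased.

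**Working it through.** The plan states no SD, effect size, interval or power, so there is no figure of its own to reproduce. The check asks how precise each possible contrast would be.

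**Inputs from the documents.** 24 dyads at 2:1 give 16 v 8.

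**Assumptions.**
- Baseline and follow-up SDs are equal.
- The baseline-to-follow-up correlation rho is not given, so 0.3 / 0.5 / 0.7 are used.
- A loss scenario of 13 v 6 (19/24 = 79%) is of the same order as the 80% benchmarks in Table 1. It is only illustrative. The retention benchmark counts sessions, and the data-collection benchmark concerns "planned assessments collected among intervention completers", so neither gives outcome availability in the control arm.

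**Interval for a bare d.** SE factor = sqrt(1/n1 + 1/n0) = sqrt(1/16 + 1/8) = 0.4330, and sqrt(1/13 + 1/6) = 0.4935. For d = 0.5, t = 0.5/0.4330 = 1.155 on 22 df and 0.5/0.4935 = 1.013 on 17 df. Inverting the noncentral t distribution gives 95% CIs of:
- 16 v 8: -0.37 to 1.36
- 13 v 6: -0.49 to 1.47

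**95% half-widths of the between-arm difference, in SD units.**
- Follow-up scores: t(N-2) x SE = 2.074 x 0.4330 = 0.898; 2.110 x 0.4935 = 1.041.
- Change scores: the above x sqrt(2(1 - rho)).
- Baseline-adjusted (ANCOVA): t(N-3) x SE x sqrt((1 - rho^2)(1 + 1/(N-4))), with t(21) = 2.080 and t(16) = 2.120.

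| Contrast | 16 v 8: rho 0.3 / 0.5 / 0.7 | 13 v 6: rho 0.3 / 0.5 / 0.7 |
|---|---|---|
| Follow-up | 0.90 / 0.90 / 0.90 | 1.04 / 1.04 / 1.04 |
| Change | 1.06 / 0.90 / 0.70 | 1.23 / 1.04 / 0.81 |
| Baseline-adjusted | 0.88 / 0.80 / 0.66 | 1.03 / 0.94 / 0.77 |
| Narrower than follow-up by | 2% / 11% / 27% | 1% / 10% / 26% |
| Narrower than change by | 17% / 11% / 5% | 16% / 10% / 4% |

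Simulation of 40,000 trials per cell gave root-mean-square half-widths for the adjusted contrast of 0.881 / 0.798 / 0.659 and 1.029 / 0.936 / 0.771, with coverage of 94.9% to 95.1%.

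**Where adjustment is best.** Let k = (1 + 1/(N-4)) x (t(N-3)/t(N-2))^2, which is 1.056 at 16 v 8 and 1.077 at 13 v 6. Adjustment beats follow-up scores when rho > sqrt(1 - 1/k) = 0.23 (0.27), and beats change scores when rho < 2/k - 1 = 0.89 (0.86). At rho = 0 it is slightly worse than follow-up scores: 0.92 v 0.90 at 16 v 8.

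**Effect of the SD chosen.** A between-arm difference of 0.5 SD divided by the change-score SD reads as 0.5/sqrt(2(1 - rho)) = 0.42 / 0.50 / 0.65.

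**If a behavior is scored as meeting or not meeting a recommendation.** The preliminary data are summarized this way ("only 34% of our sample meet this recommendation per parent report"), so it is possible in the trial. With invented counts of 8/16 v 3/8, the risk difference is 0.500 - 0.375 = 12.5 points, with a Newcombe 95% CI of -26 to +45.

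**The case against.** The best counter-argument is that the benefit of adjustment cannot be verified. Rho is unknown, and the plan does not say which unadjusted contrast it uses, so the 27% cannot be called the plan's loss. Against the better unadjusted contrast at 16 v 8, the gain is 2% at rho 0.3, peaks at 11% at rho 0.5 and falls to 5% at rho 0.7. It becomes a small loss below rho 0.23. Moving from about 0.90 to 0.80 SD changes no stated decision, because the only decision rules are the feasibility benchmarks in Table 1. It can also be said that planning d over time and between groups naturally means reporting it at both follow-ups, and that a reader could reconstruct an approximate interval.

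Much of this stands. The gain is modest and depends on assumptions, and both follow-ups is a reasonable reading, although the text does not say so. The 13 v 6 scenario and the binary counts are illustrations only, and the documents do not give the survey's scoring.

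Other parts do not depend on rho. The missing interval, score type and SD remain whatever the correlation is. A reader can reconstruct an interval only with the definition of d and the number analyzed per arm, and the plan commits to neither. Adjustment also removes the need to guess in advance which unadjusted score will be more precise. Having no decision rule on d limits the seriousness of the point, but it does not make an undefined estimate adequate for an aim that consists of estimation.

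**Conclusion.** The concern holds. Both copies of the analysis text leave the Aim 2 group effect without an interval, a baseline covariate or a full definition. This is an under-specified plan with a better method at hand, and it should be changed; it is not an error that invalidates the trial.

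The omissions are certain from the text. The width of the interval around a d of 0.5, from -0.37 to 1.36, follows from 16 v 8 alone under the usual normal model. The precision gain rests on equal SDs and an assumed rho. It ranges from slightly negative to about 11% against the better unadjusted contrast, and is larger only against the less suitable one. Even after adjustment the half-width is about 0.80 SD at 16 v 8 or 0.94 SD at 13 v 6 (rho 0.5), so Aim 2 stays exploratory.

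**What to change.** Replace the Cohen's d sentence in both places with the following specification.

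- **Outcomes and times:** each child behavior (Table 2 lists them as "Parent-reported child nutrition, physical activity, sedentary behavior and sleep behaviors") and each parental factor with a Table 2 instrument (knowledge, readiness, empowerment), at 3 and at 6 months.
- **Analysis set:** dyads with outcome data, by randomized arm regardless of sessions attended, with the number missing per arm and time point.
- **Continuous scores:** between-arm difference adjusted for the baseline value, by ANCOVA or by a repeated-measures model with baseline as covariate and small-sample degrees of freedom. Give the 95% CI on the raw scale and standardized by the pooled baseline SD.
- **Outcomes scored as meeting or not meeting a recommendation:** risk difference with a 95% CI, for example Newcombe.
- **Labeling:** at least 14 intervals result (4 behaviors + 3 parental factors = 7 outcomes, x 2 times). Call them exploratory and unadjusted for multiplicity, and call within-arm changes descriptive only.

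If the unadjusted d is kept, the minimum is to state its time point, score type and SD and to give its 95% CI.

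The cost is SAP wording and minor analysis work, with no new data. Adjustment uses one degree of freedom and gives a slightly wider interval than follow-up scores if rho is below about 0.23.

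### Parental factors are screened by significance and re-tested on the same 24 dyads or fewer with no multiplicity allowance, so named predictors are chance-prone and weak or moderate associations are overstated

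*Combined protocol and SAP*

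**What the plan says.** The Data Analysis paragraph (B.2.1.4) and Statistical Considerations describe the same two steps. First, parental factors are correlated one at a time with child behavior change scores, which the plan presents as exploration. Then: "Parental factors significantly associated with child behavior change will be analyzed using multiple linear regression to identify significant predictors of child health behavior". Neither section gives a significance level, a multiplicity adjustment, shrinkage, or a validation sample.

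The sample is fixed in Study Design & Methods: "We will recruit 24 parent/child dyads from the Down Syndrome Center of Western PA to participate in a pilot RCT". Behaviors are reported in four areas (nutrition, physical activity, sedentary behavior, sleep). Table 2 gives instruments for three parental factors: knowledge, readiness and empowerment. Data Analysis lists a fourth, in "parental factors (knowledge, readiness, empowerment, activation) over time and between groups", but activation has no instrument in Table 2 and is absent from the list in Statistical Considerations.

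The text below the feasibility benchmarks states a use for the results: "Data collected during this trial will inform intervention optimization to emphasize those mechanisms related to prioritized child behaviors". The background section says that "nutrition and sleep are emerging as priority areas to target for the PrO-PEAR intervention".

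**The concern.** Two separate problems arise if the rule is followed as written.

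- **Multiplicity.** Every factor is tested against every behavior at an unadjusted level, and the survivors are tested again on the same data. A factor that correlated by chance in these dyads will usually look predictive in a regression on these dyads.
- **Selection.** With so few dyads, only a large sample correlation reaches significance. A weak or moderate association is carried forward mainly in samples that exaggerate it, so its reported strength is biased upward.

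The screen also works against the purpose of a multiple regression. When one factor survives, nothing is left for it to be adjusted against. What is at stake is the choice of mechanisms for the next version of the intervention: a mechanism could be emphasized on a chance finding or an exaggerated one.

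**Working it through.** The plan gives no power figure to reproduce; the 24 dyads come from recruitment experience and clinic size.

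**Inputs from the plan.** At most 24 dyads; four behaviors; three measured factors (four if activation is counted).

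**Assumptions, because the plan is silent.** Two-sided 0.05 per test; one score per scale; one follow-up contrast; no covariates in the regression. A smaller analyzable sample of 19 is also tried (0.80 × 24 = 19.2).

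**1. Correlation needed to pass.** Critical |r| = t / √(n − 2 + t²).
- n=24: t = 2.074 on 22 df, so 2.074 / √(22 + 4.301) = 0.404.
- n=19: t = 2.110 on 17 df, so 2.110 / √(17 + 4.451) = 0.456.

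**2. Chance of at least one false hit at the screen, if tests are independent.** 1 − 0.95^k.
- k = 3 × 4 = 12: 46.0%.
- k = 3 × 2 = 6 (nutrition and sleep only): 26.5%.
- k = 4 × 4 = 16: 56.0%. This is the screen alone, not the full two-step rule.

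**3. Full two-step rule, no true association.** Simulated: screen at 0.05, then ordinary least squares on the survivors. Trials naming at least one predictor, three factors by four behaviors:

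| Factor / behavior correlation | n=24 | n=19 |
|---|---|---|
| 0 / 0 | 45.1% | 46.3% |
| 0.4 / 0 | 40.4% | 39.9% |
| 0.4 / 0.4 | 37.1% | 37.1% |

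At factor correlation 0.6 the rate falls to about 28-34%. The overall range is therefore 28-46%. With two behaviors it is about 17-27%, and with four factors about 33-56%.

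**4. Does the regression filter chance hits?** With three factors, about 95% of factors that pass by chance stay significant when factors are uncorrelated, about 80% at correlation 0.4, and 64-68% at 0.6. A lone survivor's regression p-value equals its correlation p-value when no covariate is added and the outcome is the same.

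**5. Is the screen the source of the false hits?** Without it, arm-adjusted one-factor models give at least one p<0.05 in 45.2%, 43.3% and 40.0% of null trials at n=24 (same three settings as the table). Three-factor models with arm give 43.8%, 42.2% and 39.7%. The rate comes from unadjusted testing.

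**6. Inflation through selection.**
- True r 0.30, n=24: passes 30% of the time; mean 0.51 when it passes, 0.29 over all trials.
- True r 0.30, n=19: passes 24%; mean 0.56 when it passes.
- True r 0.60, n=24: passes 90%; mean 0.62 when it passes, 0.59 over all trials.
- True r 0.70, n=24: 0.70 against 0.69.

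**7. How often one factor is left alone (n=24).** If one factor truly matters (r 0.30 or 0.40, factors correlated 0.4 or 0.6), 55-77% of the regressions run hold a single factor. If all three correlate 0.4 with behavior change, 32-37% do.

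**The case against.** The strongest reply is that this is a feasibility pilot, the correlations are presented as exploration, and missing a real mechanism may cost more than following a false lead. Much of that stands. Neither study aim depends on this analysis, and the optimization statement refers to trial data generally, not to this regression alone. But the closing step is worded as identifying significant predictors, which claims more than exploration in 24 dyads can support.

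The plan also does not say whether covariates enter the regression, and it screens on behavior change while naming behavior as what is predicted. The exact figures are therefore conditional, and more correlated factors bring them down.

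Four stronger readings are tempting and are not supported:
- **Every named factor is overstated.** True only on average, and for weak or moderate associations; at a true r of 0.6 or more the inflation is small.
- **The screen creates the false hits.** Step 5 shows similar rates without it.
- **One factor will usually be left.** This depends on how many factors truly matter and how correlated they are, which the documents do not settle.
- **The regression removes almost no chance hits.** At factor correlation 0.6 it removes about a third.

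The unstated timing of the parental factor, the choice of 3- or 6-month contrast, and the missing activation instrument are gaps in detail. They should be closed, but the conclusion does not rest on them.

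**Conclusion.** The concern holds. It is a flaw in a stated method, not merely missing detail, and it should be corrected. Under the assumptions listed, a trial with no true associations names at least one predictor about 28-46% of the time. Testing both follow-up contrasts would raise the number of tests to 24 (2 × 12), or 1 − 0.95^24 = 71% at the screen if independent. Weak and moderate associations that pass are overstated on average, 0.30 becoming about 0.51 at n=24 and 0.56 at n=19.

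Confidence is high in the direction and lower in any single figure, because the significance level, the number of tests and the correlations among measures are not given. The feasibility results and the planned effect-size estimates are unaffected.

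**What to change.** In both analysis sections:

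1. Drop the significance screen.
2. For each of the four behaviors, report the association with each measured factor (knowledge, readiness, empowerment), adjusted for randomized arm, with a 95% interval and whatever its size.
3. For each behavior, also report one pre-specified model with all three factors plus arm, with 95% intervals, so that mutual adjustment is kept. At n=24 this leaves 24 − 5 = 19 residual degrees of freedom.
4. Replace the aim of identifying significant predictors with estimating associations, labelled hypothesis-generating, and make no significance claim. If one is made, control for the 12 tests in item 2, for example by Benjamini-Hochberg. Removing the screen alone does not reduce chance hits.

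In the same edit, state whether the factor is a baseline or change value, name one follow-up contrast, and either add an instrument for activation or remove the term.

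**Cost.** Wording only, with no new data. Intervals widen by about 3% for the arm term, and for the three-factor model by about 8%, 24% or 47% at factor correlations 0, 0.4 or 0.6. A significance claim will usually not be possible. False discovery rate control is a real trade-off: detection of one true association among 12 falls from about 29% to 6% at r=0.30, and from about 72% to 33-36% at r=0.50. For that reason it is needed only if significance is claimed.
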